### **A. Resources and Research Facilities**

UCLA and Mayo Clinic are well-established tertiary neurotology centers with strong referral bases regionally and nationally. Both centers see large volumes of patients with VM annually and maintain large databases of patients previously diagnosed with VM. Members of the study teams at both sites have been involved in neurotology research and clinical practice for many years and have recently published investigations of VM as detailed in Preliminary Results. Facilities needed to carry out study procedures already exist at both sites. The Research Pharmacy at Mayo Clinic will support both sites.

### **B. Subject Selection and Recruitment**

New patients referred to UCLA or Mayo Clinic for recurrent vestibular symptoms during the time of the study will undergo diagnostic evaluations per usual clinical practice at each site. Patients who meet the selection criteria below will be invited to participate in the study. Existing databases will be screened for potentially eligible subjects. Individuals who appear to meet selection criteria will be sent a postal invitation to contact the study centers. Those who are interested will be scheduled for clinical re-evaluation and to review the study procedures and verify eligibility. New patients and individuals identified through existing databases who agree to participate will be enrolled after giving written informed consent. Others will be offered usual clinical care.

### **C. Study Plan**

The study will be conducted in accordance with the principles of Good Clinical Practice and will be approved by required institutional review boards and regulatory agencies. All subjects will give written informed consent before undergoing any study procedures. We have received a letter from the FDA indicating that our proposal meets the requirements for exemption from IND registration (appendix).

#### **1. Inclusion Criteria**

- a) Age  $\geq 18$  years and  $\leq 65$  years (the FDA-approved age range for rizatriptan therapy in adults).
- b) History that fulfills all criteria for VM as defined in Table 1, except that attacks must last at least 2 hours. (Shorter attacks will not last long enough to judge treatment response.)
- c) Episodes must have a spontaneous onset and resolution without associated hearing loss or interictal neurotologic deficits. (Patients with uncomplicated presbycusis or fully compensated peripheral vestibular deficits from illnesses unrelated to current vestibular attacks may participate if they meet all other criteria.)
- d) Other causes of vestibular symptoms ruled out by appropriate clinical investigations.
- e) Current medication list compatible with Concomitant Medications below.
- f) Able to maintain a Vestibular Symptom Diary and complete all other study procedures.

#### **2. Exclusion Criteria**

- a) Ménière's disease by AAO-HNS criteria
- b) Migraine with brainstem aura (formerly basilar-type migraine) by ICHD-3 criteria.

- c) Ischemic heart disease, coronary artery vasospasm, uncontrolled hypertension. (Potential subjects with uncomplicated mild hypertension may be enrolled if they are willing to bring their blood pressure under control within the first three months of study participation and maintain treatment throughout.)
- d) History of stroke or transient ischemic attack.
- e) History of using rizatriptan specifically to treat vestibular attacks.
- f) History of adverse response to triptans.
- g) Women who are pregnant or breastfeeding. (Women of childbearing age must be willing to use medically acceptable methods of birth control throughout the study.)
- h) Unable or unwilling to comply with study requirements for any reason.

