**2. Observation Phase.** Subjects will be followed for up to 12 months to prospectively characterize the frequency and severity of their vestibular attacks, associated symptoms, and comorbid conditions. Subjects will record data about all vestibular attacks that they experience during this period in their Vestibular Symptom Diaries (see description below). Subjects will be permitted to treat their symptoms according to usual clinical care. They will record all interventions in their Vestibular Symptom Diaries. Study personnel will review this information with subjects by telephone on a monthly basis and will inquire about interval changes in subjects' health and medications. This process will build rapport with subjects, ensure that they continue to meet inclusion/exclusion criteria, and identify comorbid conditions that could affect their safety or subsequent study treatment. Study personnel also will use these data to train subjects to reliably recognize attacks that will be appropriate for treatment with study medication when they enter the Treatment Phase of the investigation. Treatable comorbidities (e.g., mild hypertension, anxiety disorders) will be managed in coordination with subjects' primary care clinicians or relevant specialists. Patients whose comorbidities cannot be managed and patients who do not have two qualifying episodes after 12 months of observation will be disenrolled.

**3. Visit 2.** As soon as possible after subjects have their second qualifying attack, they will return to the study sites for re-evaluation. They will complete procedures in Table 2. Investigators will instruct subjects in the dosing of study medication, completion of treatment response and adverse event rating scales, and procedures for serious adverse events. Subjects will receive written information on adverse effects of rizatriptan. Women of child bearing years will have a pregnancy test to confirm they are not pregnant.

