**Table 2. Study Procedures and Rating Scales**

Procedures	Visit 1 Enrollment	Observation Phase	Visit 2 Randomization	Treatment Phase	Visit 3 End Point
Obtain informed consent	X				
Abstract medical record data	X				
Verify enrollment criteria	X				
Characterize baseline symptoms	X				
Instruct re Vestibular Symptom Diary	X		X		
Assess & stabilize comorbidity		1 st 3 months			
Review Vestibular Symptom Diary		Monthly	X	Monthly	X
Update health & medication list		Monthly	X	Monthly	X
Randomize for treatment			X		
Instruct re study treatment			X		
Dispense drug/placebo			X		
Treat 3 attacks				X	
Pregnancy Test			X		
Rating Scales					
Dizziness Handicap Inventory 	X		X		X
Anxiety Scale (GAD-7) 	X		X		X
Depression Scale (PHQ-9) 	X		X		X
Vestibular Symptom Diary		X		X	
Common Toxicity Criteria Scale 4.0 				X	
Treatment Satisfaction (TSQM) 				X	
Quality of Life Scale (SF-12) 	X		X	X	X
NEO-PI-3 Personality Inventory 	X				

**E. Outcome and Safety Measures (#1-4 mirror measures used in Phase III registration trials of rizatriptan)**

- 1. Vestibular Symptom Diary.** During Observation and Treatment Phases of the study, subjects will track the frequency of their headaches vestibular symptoms (unsteadiness/dizziness), and sensitivity to potential triggers of attacks (head/body motion, environmental stimuli, specific positions).
- 2. Common Toxicity Criteria Scale 4.0** (National Cancer Institute). A clinician-rated, comprehensive measure of toxicity from study medications in all body systems.
- 3. Treatment Satisfaction Questionnaire for Medication** (TSQM). A validated self-report measure of treatment satisfaction in four domains: effectiveness, side effects, convenience, and global satisfaction. Subjects will be asked whether they think they received rizatriptan or placebo after each dosing
- 4. Short Form 12** (SF-12). A 12-item self-report measure of health-related quality of life in six domains.
- 5. Dizziness Handicap Inventory** (DHI). A 25-item self-report of vertigo, dizziness, functional impairment, and emotional symptoms associated with vestibular symptoms.

6. **Generalized Anxiety Disorder Scale (GAD-7).** A 7-item self-report rating scale for anxiety, a common comorbidity of VM. The GAD-7 has cut-offs for clinically significant levels of anxiety symptoms.

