## **K. Timeline of Study**

During the first three months of the study, we expect to finalize data entry methods and train study personnel. Then we will begin recruitment into the Observation Phase. Patients will remain in the Observational Phase until they have two qualifying attacks or for a maximum of 12 months. These phases will continue for a total of four years. Subjects who are active in the Treatment Phase at month 57 will be scheduled for a Final Visit (Visit 3) regardless of how many attacks they have treated. We will conduct reviews every 3 months to evaluate enrollment and the flow of subjects through all parts of the study to determine whether recruitment efforts have to be extended and to examine safety data with the DSMB. Analysis of data from the Observation Phase will begin as soon as that portion of the study is closed. Interim analysis will occur at month 33. Analysis of treatment outcome data will commence after the last subject has a Final Visit.

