### **B. Procedures**

Study procedures are summarized Table 2 of the study protocol. The study involves three visits to the study sites, an Observation Phase and a Treatment Phase. At the Enrollment Visit, investigators will verify eligibility, obtain written informed consent, and gather initial data. Subjects will complete the self-report measures listed in Table 2. This visit is expected to last 2-3 hours. After the Enrollment Visit, subjects will enter up to a 12 month Observation Phase during which they will record descriptive data and ratings for each vertigo attack that they suffer, along with associated symptoms and treatments. The research coordinator will contact subjects on a monthly basis to review these data. Phone interviews are expected to last less than 30 minutes. During the Observation Phase, investigators will prospectively evaluate patients for comorbid medical and psychiatric conditions. Investigators will treat these conditions themselves or enlist the care of relevant medical specialists as indicated. Subjects may return to the study centers for ad hoc visits, if needed for additional evaluations. Subjects will continue in the observation period until they have two vestibular attacks that meet the inclusion criteria or until the 12 months are up.

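### A subject with mild hypertension that is not yet controlled can reach randomization inside the three-month control window, because no blood pressure reading or control condition is attached to Visit 2

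*Combined protocol and SAP*

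**What the plan says.** All references are to the combined protocol and SAP.

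- **Entry (III.C.2, item c).** Uncontrolled hypertension is an exclusion. In parentheses, those with mild, uncomplicated disease "may be enrolled if they are willing to bring their blood pressure under control within the first three months of study participation"; they must then stay on treatment.
- **Visit 2 timing (III.D.3).** "As soon as possible after subjects have their second qualifying attack, they will return to the study sites for re-evaluation".
- **Length of observation.** III.K: "Patients will remain in the Observational Phase until they have two qualifying attacks or for a maximum of 12 months". IV.B: "Subjects will continue in the observation period until they have two vestibular attacks that meet the inclusion criteria or until the 12 months are up". Both give a maximum and neither gives a minimum.
- **Table 2.** The row "Assess & stabilize comorbidity" is marked for the first three months of observation and not at Visit 2. Randomization and the row "Dispense drug/placebo" are marked at Visit 2. Verification of enrollment criteria is marked at Visit 1 only. There is no row for blood pressure or vital signs.
- **Conditions for randomization (IV.B).** Two attacks of at least moderate severity, and acceptable adherence to data collection.
- **General safeguards.** Monthly calls are meant to "ensure that they continue to meet inclusion/exclusion criteria" (III.D.2). For comorbid conditions, "Investigators will treat these conditions themselves or enlist the care of relevant medical specialists as indicated" (IV.B). Subjects whose comorbidities cannot be managed are disenrolled (III.D.2). Doses for comorbid conditions must be stable before the Treatment Phase and stay unchanged through it (III.G). Drug is released on a physician investigator's prescription (III.F).

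**The concern.** The control period runs forward from study entry, while the date of first drug supply is set by attack timing. Nothing links the two. Entry under the allowance depends on willingness, so a subject who has not yet reached control still satisfies the criterion until the three months are up.

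Patient safety is at stake. Sections I.E and IV.E.1 give vasospasm and cardiac complications as the reasons for keeping triptans from people with uncontrolled hypertension. Study drug is taken at home, and IV.B notes that three attacks could be treated within as little as six days. All three doses could therefore fall before the control period ends.

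**Working it through.** The plan states no figure on this point, so there is none to reproduce. The check has two parts.

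**1. Does any rule stop an uncontrolled subject at Visit 2?**

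| Rule | What it requires | Does it stop a subject on a fixed dose, or on no drug, who is uncontrolled and inside three months? |
|---|---|---|
| Exclusion c with its allowance (III.C.2) | Willingness to reach control by month 3 | No; the criterion is met |
| Monthly eligibility review (III.D.2) | Continued fit with the criteria, by telephone | No; the criteria are still met, and no measurement is named |
| Disenrollment (III.D.2) | Comorbidity that cannot be managed | No; it is being managed but is not yet controlled |
| Stable doses (III.G) | No dose changes | No; it governs doses, not response |
| Visit 2 procedures (III.D.3, Table 2) | Re-evaluation, health and medication update, pregnancy test | Only at the investigator's discretion |
| Randomization conditions (IV.B) | Two attacks and adherence | No |

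On III.G, a subject whose antihypertensive dose is still being adjusted is barred outright. The gap is confined to subjects with no dose change under way.

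The plan handles comparable conditions more tightly. Depression is also allowed three months to come under control, but it is measured at Visits 1, 2 and 3, with a PHQ-9 cut-off above 9, a physician examination at the visit and disenrollment if the subject is judged ineligible (IV.D.4). Pregnancy is tested at Visit 2.

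**2. Is a Visit 2 inside three months plausible?**

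The documents give no attack rate. Assume that the forecast of 50% of enrolled subjects randomized (III.L) reflects two attacks within 12 months. The results abstract at the end of the document is close to this: 114/225 = 50.7%.

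*One common attack rate (Poisson).* With m the expected number of attacks in a period, P(at least 2) = 1 − exp(−m)(1 + m). Setting this to 0.50 at 12 months gives m = 1.678, or 1.678/12 = 0.140 per month. The share of randomized subjects whose Visit 2 falls inside three months is P(at least 2 by month 3 − d)/0.50, where d is the delay in months from attack to visit.

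*Rates varying between subjects (gamma, shape 1; an assumption).* P(at least 2) = [m/(1 + m)]². Setting this to 0.50 at 12 months gives a mean m = 2.414. At three months m = 2.414/4 = 0.604, and (0.604/1.604)² = 0.142.

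| Delay d | Common rate | Gamma rates |
|---|---|---|
| 0 | 0.0669/0.50 = 13% | 0.1417/0.50 = 28% |
| 0.5 month | 0.0486/0.50 = 10% | 0.1120/0.50 = 22% |
| 1 month | 0.0325/0.50 = 7% | 0.0823/0.50 = 16% |

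With no delay, gamma shapes 2 and 0.5 give 21% and 43%. If 60% rather than 50% have two attacks, because some are not randomized for other reasons, the common-rate figure with no delay is 15%.

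These shares cover all randomized subjects. To count affected subjects one would also need the share enrolled with mild hypertension and the share of those still uncontrolled, with no dose change under way, at an early Visit 2. The documents give neither.

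**The case against.** The best reply is that the plan, read as a whole, places control before treatment. Uncontrolled hypertension is excluded in III.C.2, and IV.E.1 repeats this without qualification. The parenthesis can be read as an enrollment allowance with an outer limit, not as permission to dose. III.D.2 names mild hypertension among the comorbidities to be managed during observation, and III.L expects hypertension to be stabilized then. III.G keeps out anyone still being titrated. Visit 2 is an in-person re-evaluation, and a physician must write the prescription. Subjects with conditions incompatible with rizatriptan are withdrawn (III.H). The group is mild and uncomplicated, and exposure is limited to single 10 mg doses for at most three attacks.

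Most of this stands. It establishes the intent, removes the titration case and makes the remaining case small. A reader might infer that the plan authorizes dosing of subjects with uncontrolled hypertension, or of subjects whose treatment is still being adjusted. The documents do not support either: the first runs against III.D.2, III.L and IV.E.1, and the second against III.G.

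What the reply does not supply is a rule that gives effect to the intent at Visit 2. Telephone calls cannot measure blood pressure, the re-evaluation has no stated blood pressure content, and no definition of control is given. Protection in the remaining case depends on an investigator choosing to check.

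**Conclusion.** The gap is real but narrow. Followed as written, the plan allows rizatriptan to be dispensed to a subject with mild hypertension who is on a fixed dose or managed without drugs, is not yet controlled, and reaches a second attack within three months of entry. This rests on the absence of any minimum observation time and of any blood pressure reading or control condition at Visit 2.

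The number affected is unknown and probably small, since several conditions must coincide. It would be tempting to read the 7% to 28% range as the share of hypertensive subjects dosed while uncontrolled. The documents do not support that: the figures describe all randomized subjects, rest on assumed attack rates, and take attack timing to be unrelated to blood pressure. They show only that an early Visit 2 is a realistic event. The good tolerability reported in the results abstract does not settle the matter, because the abstract says nothing about blood pressure at dosing.

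No effect on the efficacy estimate, power or type I error is claimed. This is an inexpensive patient-safety improvement.

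**What to change.** 1. Add a blood pressure row to Table 2, marked at Visit 1 and at Visit 2 before randomization.
2. Require documented control, by a threshold the sponsor sets, before randomizing anyone enrolled under the mild-hypertension allowance.
3. If the second attack comes first, keep the subject in the Observation Phase until control is documented, and disenroll if it is not reached by three months.
4. State this as an exception to the timing rules in III.D.3, III.K and IV.B, and add it to the randomization conditions in IV.B.

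The cost is a few minutes with a cuff at two visits that already take place, one table row and one eligibility condition. The downside is that a few subjects are delayed or found ineligible. The sample size calculation in III.J.1 is unchanged.

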#### **D. Study Visits and Phases**

**1. Visit 1.** Prior to study entry, potential subjects will be evaluated clinically, including neurologic history, examination, and laboratory testing per usual practice at each site. These steps will be part of routine clinical care, not study procedures. Study personnel will identify potential subjects (i.e., those diagnosed with VM) by contacting treating clinicians and providing information pamphlets to patients at each site. Interested patients will be invited to Visit 1 where the study will be reviewed with them in detail. Those who elect to participate will provide written informed consent. Investigators will then abstract baseline data from their medical records including demographics, medical history, list of allergies and current medications, family history, and results of neurologic examinations and testing. Subjects will be asked to provide detailed descriptions of all symptoms experienced during vestibular attacks, which will be recorded verbatim. If this information fulfills all inclusion and exclusion criteria, subjects will be instructed in procedures for the Observation Phase, including use of the Vestibular Symptom Diary. Subjects also will complete the symptom self-report measures listed in Table 2.

**2. Observation Phase.** Subjects will be followed for up to 12 months to prospectively characterize the frequency and severity of their vestibular attacks, associated symptoms, and comorbid conditions. Subjects will record data about all vestibular attacks that they experience during this period in their Vestibular Symptom Diaries (see description below). Subjects will be permitted to treat their symptoms according to usual clinical care. They will record all interventions in their Vestibular Symptom Diaries. Study personnel will review this information with subjects by telephone on a monthly basis and will inquire about interval changes in subjects' health and medications. This process will build rapport with subjects, ensure that they continue to meet inclusion/exclusion criteria, and identify comorbid conditions that could affect their safety or subsequent study treatment. Study personnel also will use these data to train subjects to reliably recognize attacks that will be appropriate for treatment with study medication when they enter the Treatment Phase of the investigation. Treatable comorbidities (e.g., mild hypertension, anxiety disorders) will be managed in coordination with subjects' primary care clinicians or relevant specialists. Patients whose comorbidities cannot be managed and patients who do not have two qualifying episodes after 12 months of observation will be disenrolled.

**3. Visit 2.** As soon as possible after subjects have their second qualifying attack, they will return to the study sites for re-evaluation. They will complete procedures in Table 2. Investigators will instruct subjects in the dosing of study medication, completion of treatment response and adverse event rating scales, and procedures for serious adverse events. Subjects will receive written information on adverse effects of rizatriptan. Women of child bearing years will have a pregnancy test to confirm they are not pregnant.

**4. Treatment Phase.** Subjects who qualify for randomization will enter the Treatment Phase. They will be randomly assigned to parallel study arms in a 2:1 ratio of rizatriptan 10 mg encapsulated tablets or look-alike placebo capsules. Subjects will treat three vestibular attacks that manifest with Grade 3/2 vestibular symptoms. Associated symptoms, including headache, need not be present and may be of lesser severity. Headaches without vestibular symptoms are not eligible for study treatment, but may be treated in the subjects' usual manner. Subjects will be instructed to ingest one study capsule as soon as possible after onset of Grade 3/2 vestibular symptoms. They will record treatment response in their Vestibular Symptom Diaries by rating the severity of vestibular and associated symptoms at the time they take study medication and at 0.5, 1, 2, 4, 24, and 48 hours post-dose. Subjects will record adverse effects in accordance with the Common Toxicity Criteria Scale 4.0, treatment satisfaction on the TSQM, and quality of life on the SF-12 at 48 hours post-dose. Then they will contact study personnel by phone to review the attack and treatment response.

Subjects will treat one attack with study medication in a 48-hour period. Repeat dosing of study medication within 48 hours will not be permitted. Subjects must have a vertigo-free period of at least 48 hours before treating a subsequent vestibular attack with study medication. The relatively short plasma half-life of rizatriptan (2-2.5 hours) justifies the 48-hour wash out period. Subjects may use other medications to treat residual symptoms (see Concomitant Medications) but must wait at least 1 hour after taking the study medication. Additional treatments will be reported to study personnel together with other attack data. Subjects will remain in the Treatment Phase until they have treated three separate vestibular attacks, experience serious or intolerable adverse effects, withdraw for other reasons, or reach the end of the study. Study personnel will conduct telephone assessments on a monthly basis as they did during the Observation Phase. Extra visits to study clinics will be arranged as needed to re-evaluate subjects' health and treat problematic symptoms.

**5. Visit 3.** Subjects will return to their study center as soon as possible after treating their third attack with study medication, preferably within two weeks of their last treated attack. They will complete rating scales listed in Table 2 and review their Vestibular Symptom Diaries with study personnel. Arrangements will be made for follow-up clinical care, and subjects will be discharged from the study.

